6.1.1. Calculation of CDAI and PRO2 Scores

The CDAI system is a composite index of 8 disease activity variables (components) with scores ranging from 0 to over 600 based upon a composite of symptoms (eg, abdominal pain), signs (the presence of abdominal mass and body weight), laboratory values (eg, hematocrit), and physician assessment amongst others. The CDAI has 3 patient reported outcome components: liquid or very soft stool frequency, abdominal pain, and general wellbeing. The clinical remission by CDAI endpoint is defined by the CDAI score, calculated as a weighted sum of all 8 component subscores.

If subjects have 3 or more of the 8 component subscores missing, then the subjects will be considered as having insufficient data to determine response status and their CDAI score will be considered missing. If subjects have 1 or 2 CDAI components missing, then the missing component will be imputed by the Last Observation Carrying Forward (LOCF) method using the previous valid component score calculated at the most recent analysis visit (eg, use the component score from Week 6 to impute missing component at Week 10, or use the component score from Week 18 to impute missing component at Week 24). If the component score from the most recent analysis visit is also missing, the missing value will be imputed with corresponding component score at baseline.

The PRO2 has 2 patient reported outcome components: liquid or very soft stool frequency subscore and abdominal pain subscore. If either subscore is missing, no imputation will be done.

For further information on CDAI, PRO2, and calculation rules at screening and post-screening, refer to [Appendix 3](#).

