1.3. Sample Size and Power

A sample size of 40 subjects in each of the filgotinib treatment groups and 20 subjects in the placebo group is considered adequate to assess the safety, tolerability, and efficacy of filgotinib in a descriptive manner. Assuming a clinical remission rate of 40% for the filgotinib treatment groups (200 mg and 100 mg), the 2-sided 90% exact confidence interval is (26.9%, 54.2%). The clinical remission rate for placebo group is assumed to be 20%.

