6. EFFICACY ANALYSES

6.1. General Considerations

[figure not shown]
The efficacy analysis will be conducted on the FAS, defined in Section 3.1.2, unless otherwise specified.

The definitions of dichotomous efficacy endpoints are provided in [Table 6-1, Appendix 6](#) includes a detailed definition of study treatment failure and the corresponding data handling rules for efficacy analysis.

Table 6-1. Definitions of Dichotomous Efficacy Endpoints

Type	Endpoint	Definition
Primary	Clinical remission by CDAI at Week 24	CDAI score < 150 points at Week 24
Secondary	MaRIA remission in terminal ileum segment at Week 24	MaRIA score < 7 in terminal ileum segment at Week 24 among subjects with MaRIA score ≥ 7 in the same segment at Baseline
Secondary	MaRIA remission in distal ileum segment at Week 24	MaRIA score < 7 in distal ileum segment at Week 24 among subjects with MaRIA score ≥ 7 in the same segment at Baseline
Secondary	MaRIA remission in jejunum segment at Week 24	MaRIA score < 7 in jejunum segment at Week 24 among subjects with MaRIA score ≥ 7 in the same segment at Baseline
Secondary	MaRIA response in terminal ileum segment at Week 24	Among subjects with Baseline MaRIA score ≥ 7 in terminal ileum: 
if baseline MaRIA score ≥ 11, a segmental MaRIA score < 11, or a decrease from baseline in segmental MaRIA score \geq MDD in terminal ileumif baseline MaRIA score < 11, a segmental MaRIA score < 7, or a decrease from baseline in segmental MaRIA score \geq MDD in terminal ileum
Secondary	MaRIA response in distal ileum segment at Week 24	Among subjects with Baseline MaRIA score ≥ 7 in distal ileum: 
if baseline MaRIA score ≥ 11, a segmental MaRIA score < 11, or a decrease from baseline in segmental MaRIA score \geq MDD in distal ileumif baseline MaRIA score < 11, a segmental MaRIA score < 7, or a decrease from baseline in segmental MaRIA score \geq MDD in distal ileum

Type	Endpoint	Definition
Secondary	MaRIA response in jejunum segment at Week 24	
Among subjects with Baseline MaRIA score ≥ 7 in jejunum:
 
 if baseline MaRIA score ≥ 11, a segmental MaRIA score < 11, or a decrease from baseline in segmental MaRIA score \geq MDD in jejunum if baseline MaRIA score < 11, a segmental MaRIA score < 7, or a decrease from baseline in segmental MaRIA score \geq MDD in jejunum

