Appendix 3. Crohn's Disease Activity Index (CDAI) and Patient Reported Outcomes – 2 items (PRO2)

The CDAI score is a weighted sum of all 8 variables as specified in [Table 13-1](#). The PRO2 scores will be assessed according to [Table 13-2](#). Details for the calculations of CDAI and PRO2 scores at screening and post-screening visits are provided in this appendix.

Table 13-1. Calculation of CDAI Score

Variable no.	Variable	Variable description	Multiplier
1	Liquid or very soft stool	Daily stool count is summed for 7 days	2
2	Abdominal pain	Sum of 7 days of daily ratings as 0 = none, 1 = mild, 2 = moderate, 3 = severe	5
3	General wellbeing	Sum of 7 days of daily ratings as 0 = generally well, 1 = slightly below par, 2 = poor, 3 = very poor, 4 = terrible	7
4	Complications	Number of listed complications: Arthritis or arthralgia Erythema nodosum, pyoderma gangrenosum or aphthous stomatitis Iritis or uveitis Anal fissures or fistulae or abscess Other fistula Fever over 37.8 C [100 F] during past week	20 each
5	Use of anti-diarrheal medications	Use of diphenoxylate or loperamide or other opiate for diarrhea 0 = No, 1 = Yes	30
6	Abdominal mass	0 = none, 2 = questionable, 5 = definite	10
7	Hematocrit*	Males: 47 – Hct [%] Females: 42 – Hct [%] *Result must be greater than or equal to 0. If negative result enter 0	6 × difference
8	Weight*	Percentage deviation from standard weight $(1 - \text{weight} / \text{standard weight}) \times 100$ *Limit of -10 (Result must be greater than or equal to -10)	1
CDAI score			TOTAL

CDAI = Crohn's Disease Activity Index; Hct = hematocrit
{Sandborn 2002}

Table 13-2. Calculation of PRO2 Components

Variable no.	Variable	Variable Description
1	Liquid or very soft stool	Mean of the daily (liquid or very soft) stool count for 7 days
2	Abdominal pain	Mean of 7 days of daily ratings as 0 = none, 1 = mild, 2 = moderate, 3 = severe

{Khanna 2015}

Each PRO2 subscore will be rounded to the nearest integer (eg, 2) for calculation of endpoints.

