Rounding of subscores into one decimal place is for displaying purpose only. When calculating the CDAI scores, the subscores will not be rounded.

- 4) The CDAI score for a specific visit is based on a weighted sum (rounded to the nearest integer) of all 8 components. The CDAI score will be set to 0 in the case the calculation leads to a CDAI score of < 0. Each component will be selected within the analysis window as defined in Section [3.7.2](#).
 - a) If subjects have 3 or more of the 8 CDAI components missing, then the subjects will be considered as having insufficient data to determine response status and their CDAI score will be considered missing. If at least 1 out of the 6 complications under the complication component is missing, then the complication component will be considered missing.
 - b) If subjects have 1 or 2 components missing, then the missing component will be imputed by the LOCF method using the previous valid component score calculated at most recent analysis visit (eg, use the component score from Week 6 to impute missing component at Week 10, or use the component score from Week 18 to impute missing component at Week 24). If the component score from the most recent analysis visit is also missing, the missing value will be imputed with corresponding component score at baseline.
- 5) The PRO2 subscores for a specific visit are based on the evaluation of liquid or very soft stool frequency and abdominal pain subscores individually (rounded to the nearest integer) within the analysis window as defined in Section [3.7.2](#). If either subscore is missing, no imputation will be done.

Source of Information Used for Calculation

The sources of information used for the calculations of CDAI and PRO2 scores as described above are given in [Table 13-5](#) (the calculated scores from ERT data will not be used for data analysis). Hematocrit collected from local laboratory and weight measured at home due to COVID-19 impact will be used in CDAI calculation.

Table 13-5. Sources of Information for Calculating CDAI and PRO2 Scores

Variable in Calculation	Data Source
MRE Procedure Date	MREDAT in MRE dataset from eCRF data for Screening and Week 24
Lower Endoscopy Procedure Date	QSORRES in CDAI dataset with QSTEST “Date of Procedure” from vendor ERT data
Visit Date	VISITDAT in VISDT dataset from eCRF data
Subject Activation Date on Electronic Device	QSORRES in CDAI dataset with QSTEST “Date of Visit” and Visit “Screening” from vendor ERT data

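### One blank complication item at Week 24 lets the Week 18 (or baseline) complications total replace recorded answers, which can reverse a remission status those answers already settle

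*SAP*

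**What the plan says.** SAP Table 13-1 (Appendix 3) scores component 4 as the "Number of listed complications", six in all, at 20 points each. Three rules then act in sequence.

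- **When the component is missing.** Appendix 3, post-screening step 4a: "If at least 1 out of the 6 complications under the complication component is missing, then the complication component will be considered missing".
- **What replaces it.** If one or two of the eight components are missing, Section 6.1.1 states that "the missing component will be imputed by the Last Observation Carrying Forward (LOCF) method using the previous valid component score"; step 4b says the same. The example given for the primary time point is to "use the component score from Week 18 to impute missing component at Week 24". If that score is missing as well, "the missing value will be imputed with corresponding component score at baseline".
- **When imputation stops.** "If subjects have 3 or more of the 8 CDAI components missing", the whole CDAI is missing. The subject then counts as a non-responder under the non-responder imputation rule in Section 6.1.

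Neither document says to keep the answered complication items, to impute item by item, or to check the imputed score against what was recorded. Section 6.3.2 applies the same component carry-forward to the CDAI-change analyses.

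**The concern.** A form with five answers and one blank still holds nearly all the information in the component: the unanswered item can add only 0 or 20 points. The rule discards the five answers and substitutes a total from another visit. The resulting CDAI can be one that the subject's own Week 24 record excludes.

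Non-responder imputation does not catch this, because one or two missing components lead to carry-forward and not to a missing CDAI. The plan is also uneven. For the three diary components, Appendix 3 uses partial data once four evaluable days are available. For complications it drops five answers of six, and gives no reason.

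The score feeds the primary endpoint, Week 10 remission and the change in CDAI at Weeks 10 and 24. The study is descriptive, so the estimated proportions and their 90% intervals are the result.

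**Working it through.** **Inputs.** Six items at 20 points each (SAP Table 13-1). Primary endpoint "CDAI score < 150 points at Week 24" (SAP Table 6-1). "A sample size of 40 subjects in each of the filgotinib treatment groups and 20 subjects in the placebo group", with assumed remission of 40% on filgotinib and 20% on placebo (SAP Section 1.3). Missingness and carry-forward rules as set out above.

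**The plan's own figure.** 40% of 40 is 16 remitters. The 90% Clopper-Pearson interval for 16/40 is 26.9% to 54.2%, as SAP Section 1.3 states. That figure is not in dispute.

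**Notation, with one item blank.** S is the weighted total of the other seven components, k the number of complications recorded present among the five answered items, and c the complication count carried forward.

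- Possible true CDAI: S + 20k or S + 20k + 20.
- CDAI under the SAP rule: S + 20c.
- Non-remission is settled by the record if S + 20k ≥ 150.
- Remission is settled by the record if S + 20k + 20 < 150, that is S ≤ 129 − 20k.

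**Where the rule reverses a settled status (S in whole points).**

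- False remission needs 150 − 20k ≤ S ≤ 149 − 20c. This is possible only if c ≤ k − 1.
- False non-remission needs 150 − 20c ≤ S ≤ 129 − 20k. This is possible only if c ≥ k + 2.

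| Recorded yes (k) | Carried (c) | Reversal | Band for S |
|---|---|---|---|
| 1 | 0 | false remission | 130 to 149 |
| 2 | 0 | false remission | 110 to 149 |
| 2 | 1 | false remission | 110 to 129 |
| 0 | 2 | false non-remission | 110 to 129 |
| 0 | 3 | false non-remission | 90 to 129 |
| 1 | 3 | false non-remission | 90 to 109 |

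**Two cases.**

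- S = 125, two complications recorded, one item blank, none at Week 18. True CDAI is 125 + 40 = 165 or 125 + 60 = 185, so not remission. The rule gives 125 + 0 = 125, so remission.
- S = 115, five items recorded absent, one blank, two complications at Week 18. True CDAI is 115 or 115 + 20 = 135, so remission. The rule gives 115 + 40 = 155, so not remission.

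**Item-level carry-forward.** Keeping the answers and filling only the blank with 0 or 1 gives S + 20k or S + 20k + 20, which are the only two possible true values. A settled status therefore cannot be reversed. Enumeration over S from 0 to 299 and k from 0 to 5 gives zero reversals.

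**Size of one reversal.** 1/40 = 2.5 points; 1/20 = 5 points.

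| Remitters | Rate | 90% exact interval |
|---|---|---|
| 15/40 | 37.5% | 24.7% to 51.7% |
| 16/40 | 40.0% | 26.9% to 54.2% |
| 17/40 | 42.5% | 29.2% to 56.7% |
| 4/20 | 20.0% | 7.1% to 40.1% |
| 5/20 | 25.0% | 10.4% to 45.6% |

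For the difference the SAP names no interval method, so a 90% Wald interval serves as illustration. The assumed 20.0 points (0.5 to 39.5) becomes 15.0 (−5.4 to 35.4) with one extra placebo remission, or 17.5 (−1.9 to 36.9) with one fewer filgotinib remission.

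**The case against.** The strongest reply is that this is a clear, programmable convention, that protocol Section 8.3 leaves missing CDAI data to the SAP, and that the trigger will seldom occur.

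- **Rarity.** Protocol Section 6.3 requires the non-patient-reported CDAI variables at every visit and describes electronic capture before central calculation. That makes a partly blank form less likely, though nothing says each item is mandatory, and the SAP did write a rule for the case. This stands as a limit on frequency.
- **Another record in the window.** Appendix 3 step 4 selects each component within the analysis window (Days 142 to 197 for Week 24), and Section 3.7.3 selects among nonmissing values. A complete complications record elsewhere in the window could arguably be used before any carry-forward. This stands, but few subjects may have a second assessment.
- **Several conditions must coincide.** A reversal needs a partly blank form, at most two missing components, a mismatched carried count, and S in the band shown. This stands.
- **Descriptive study.** There is no formal test, and one subject shifts an arm by little against intervals this wide. True, but it does not justify a score that the record contradicts.

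Three stronger readings are tempting, and the documents do not support them. A reader might infer that 100 points of recorded data (5 × 20) are typically at risk. That is a ceiling needing all five answered items present, and exclusion criteria 7 and 15 make the fistula and abscess items unlikely at entry. A reader might infer that the rule favours filgotinib. Reversals run both ways and no frequency by arm is given. Finally, a blank item together with missing hematocrit and weight makes the CDAI missing, and this might look like a further defect. Treating three incomplete components as insufficient data is consistent with the plan's non-responder principle.

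**Conclusion.** The concern holds in a limited form. As written, the rule can contradict a remission status that the Week 24 record already settles: false remission when the carried count is below the recorded count, false non-remission when it is at least two above. In each case the other seven components must lie in a limited band. The analysis rests on at most two missing components, no complete complications record available in the window, and a carried value from Week 18 or, failing that, baseline.

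Each affected subject moves a filgotinib arm by 2.5 percentage points or the placebo arm by 5. How many subjects that would be cannot be computed from the documents; it is probably few. The change is worth making because the error is avoidable and reaches the primary endpoint. Nothing here shows that the trial's conclusions would change.

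**What to change.** In SAP Appendix 3 step 4b and Section 6.1.1, state that when the complications component is imputed, every item recorded at the visit is kept. Only the blank item or items are carried forward, from the most recent analysis visit, with the existing baseline fallback. Apply the same rule to Week 10 remission and to the CDAI-change imputation in Section 6.3.2.

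Leave step 4a's 3-of-8 count unchanged, so that a component with any blank item still counts as missing for data sufficiency. Counting it as missing only when all six items are blank would loosen that safeguard on the primary endpoint: with five blanks, up to 100 points could be carried forward while the component passed as observed.

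The cost is about two sentences and a few lines of code. Step 4a already works from item-level missingness, so no new data are needed. No clinical procedure, threshold or endpoint changes. The edit belongs in the SAP before it is finalized; after that, SAP Section 1 requires the change to be documented in the CSR.

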6.1.2. Calculation of MaRIA Scores and Corresponding Endpoints

The MaRIA scoring system is a composite index of 4 components. These components are edema, ulcers, gut wall thickness, and relative contrast enhancement (RCE). A segmental MaRIA score can be calculated at Screening (used as the baseline) and Week 24 as a weighted sum of these 4 components for each of the 3 small bowel segments (terminal ileum, jejunum, and duodenum).

For segment level remission or response based on MaRIA score, if a bowel segment that was identified at baseline has a segmental MaRIA score missing at Week 24, no imputation will be done and the subject will be considered as having insufficient data to determine segment level remission or response status and treated as a non-responder in that specific segment.

For subject level remission or response based on MaRIA score, if more than one small bowel segment that was identified at baseline is missing at Week 24, the subject will be considered as having insufficient data to determine remission or response status and will be considered as a non-responder. If only one small bowel segment that was identified at baseline is missing at Week 24, then LOCF will be used to impute the missing segment. Small bowel segments with missing segmental MaRIA scores at baseline will not be considered when assessing subject level response status.

Detailed information on MaRIA score calculation rules are provided in [Appendix 5](#).

6.2. Primary Efficacy Endpoint

6.2.1. Definition of the Primary Efficacy Endpoint

The primary endpoint is the proportion of subjects achieving clinical remission, defined as CDAI score < 150 points at Week 24.

6.2.2. Analysis of the Primary Efficacy Endpoint

For the primary efficacy endpoint, the number and proportion of subjects achieving clinical remission by CDAI at Week 24 for each treatment group will be summarized with corresponding 90% exact confidence interval (CI) based on the binomial distribution (Clopper-Pearson method). The difference in proportions between each filgotinib dose group and the placebo group will be presented along with the associated 90% CI. No formal hypothesis testing will be performed. Bar-chart of proportions of subjects achieving clinical remission at Week 24, defined as CDAI score < 150 points, will be provided by treatment group.

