### **Study Design:**

This is a Phase 2 randomized, double-blind, placebo-controlled study to evaluate the efficacy and safety of filgotinib in treating subjects with SBCD. Approximately 100 subjects aged 18 to 75 years with SBCD will be randomized to 1 of 3 treatment groups in a 2:2:1 ratio.

FIL filgotinib; PBO placebo; mg milligram.

\* Non responders are subjects who never achieved a  $\geq 70$  point CDAI reduction from baseline or CDAI  $< 150$  at any point up to and including Week 10

\*\* Disease worsening is defined as a  $\geq 100$  point increase in CDAI score from the Week 10 value and CDAI score  $\geq 220$  points at 2 consecutive visits

value  
CCI

**Treatment group 1 (n = 40):** Filgotinib 200 mg and placebo-to-match (PTM) filgotinib 100 mg, once daily

**Treatment group 2 (n = 40):** Filgotinib 100 mg and PTM filgotinib 200 mg, once daily

**Treatment group 3 (n = 20):** PTM filgotinib 200 mg and PTM filgotinib 100 mg, once daily

Note: United States (US) males who have not failed at least 2 prior biologic therapies (any tumor necrosis factor-alpha (TNF $\alpha$ ) antagonist and vedolizumab) will be randomized in a 2:1 ratio to either filgotinib 100 mg or matching placebo.

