1.2. Study Design

[figure not shown]
This is a Phase 2 randomized, double-blind, placebo-controlled study to evaluate the efficacy and safety of filgotinib in treating subjects with SBCD. A schematic of this study is provided in [Figure 1-1](#). Subjects who meet protocol eligibility criteria will be randomized in a blinded fashion to 1 of 3 treatment groups in a 2:2:1 ratio:

- **Treatment group 1 (n = 40):** Filgotinib 200 mg and placebo-to-match (PTM) filgotinib 100 mg, once daily
- **Treatment group 2 (n = 40):** Filgotinib 100 mg and PTM filgotinib 200 mg, once daily
- **Treatment group 3 (n = 20):** PTM filgotinib 200 mg and PTM filgotinib 100 mg, once daily

Note: United States (US) males who have not failed at least 2 prior biologic therapies (ie, any tumor necrosis factor-alpha [TNF α] antagonist and vedolizumab) will be randomized in a 2:1 ratio to receive either filgotinib 100 mg or matching placebo.

Figure 1-1.

Study Design Schematic

FIL filgotinib; PBO placebo; mg milligram.

*Non responders are subjects who never achieved a ≥ 70 point CDAI reduction from baseline or CDAI < 150 at any point up to and including Week 10

**Disease worsening is defined as a ≥ 100 point increase in CDAI score from the Week 10 value and CDAI score ≥ 220 points at 2 consecutive visits

CCI

Treatment assignments will be stratified according to the following factors:

- Concomitant use of oral, systemically absorbed corticosteroids (eg, prednisone) at Day 1, (Yes or No)
- Concomitant use of immunomodulators (eg, 6-mercaptopurine [6-MP], azathioprine, methotrexate [MTX]) at Day 1, (Yes or No)
- Prior exposure to biologics (eg, TNF α antagonists or vedolizumab), (Yes or No)

This study includes:

- Screening (Days -30 to -1)
- Randomization (Day 1)

- Blinded treatment (Day 1 to Week 24)

Efficacy assessment: At Week 24, CDAI score to assess clinical remission; MRE to assess radiographic changes

cc1 [REDACTED]

cc1 [REDACTED]

- Post-Treatment (PTx) safety assessments

cc1 [REDACTED]

cc1 [REDACTED]

cc1 [REDACTED]

- Steroid tapering must begin at Week 10 for subjects who are considered responders.

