3.3. Strata and Covariates

Subjects will be randomly assigned to treatment groups via the interactive web response system (IWRS) in a 2:2:1 ratio using a stratified randomization schedule. Stratification will be based on the following variables:

- Concomitant use of oral, systemically absorbed corticosteroids (eg, prednisone) at Day 1, (Yes or No)
- Concomitant use of immunomodulators (eg, 6-MP, azathioprine, methotrexate) at Day 1, (Yes or No)
- Prior exposure to biologics (eg, TNF α antagonists or vedolizumab), (Yes or No)

If there are discrepancies in stratification factor values between the IWRS and the clinical database (eCRF data), the values recorded in the clinical database will be used for analyses. For derivation of concomitant medication use at Day 1, the start date of such medication should be before or on the same date of the first dose of study drug and with either the stop date of such medication being on or after the first dose of study drug or with “ongoing” status.

Efficacy endpoints will be evaluated using stratification factors as covariates or stratification variables for analyses, as specified in Section 6.

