3.4. Examination of Subject Subgroups

There are no prespecified subject subgroupings for efficacy and safety analyses.

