4. SUBJECT DISPOSITION

4.1. Subject Enrollment and Disposition

A summary of subject enrollment will be provided by treatment group for each country, investigator within a country, and overall. The summary will present the number and percentage of subjects enrolled. For each column, the denominator for the percentage calculation will be the total number of subjects analyzed for that column.

A similar enrollment table will be provided by randomization stratum. The denominator for the percentage of subjects in the stratum will be the total number of enrolled subjects within that stratum. If there are discrepancies in the value used for stratification assignment between the IWRS and the clinical database, the value collected in the clinical database will be used for the summary. A listing of subjects with discrepancies in the value used for stratification assignment between the IWRS and the clinical database at the time of data finalization will be provided.

The randomization schedule used for the study will be provided as an appendix to the CSR.

A summary of subject disposition will be provided by treatment group and overall. This summary will present the number of subjects screened, the number of subjects who met all eligibility criteria but were not randomized with reasons subjects not randomized, the number of subjects randomized, and the number of subjects in each of the categories listed below:

- All Randomized Analysis Set
- Full Analysis Set
- Safety Analysis Set
- [REDACTED]
- [REDACTED]
- Completed study drug
- Did not complete study drug with reasons for premature discontinuation of study drug
- Completed study
- Did not complete the study with reasons for premature discontinuation of study

For the status of study drug and study completion and reasons for premature discontinuation, the number and percentage of subjects in each category will be provided. The denominator for the percentage calculation will be the total number of subjects in the Safety Analysis Set corresponding to that column.

The following by-subject listings will be provided by subject identification (ID) number in ascending order to support the above summary tables:

- Reasons for premature study drug or study discontinuation (A separate listing of reasons for premature study drug or study discontinuation due to COVID-19 will be created.)
- Reasons for screen failure (will be provided by screening ID number in ascending order)

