6.3.2. Analysis of the Secondary Efficacy Endpoints

For binary endpoints, the same statistical analysis methods described in Section [6.2.2](#) for analyzing the primary efficacy endpoint will be utilized.

Continuous endpoints will be summarized using descriptive statistics (n, mean, SD, median, Q1, Q3, minimum, maximum) by treatment group and analysis visit.

An analysis of covariance (ANCOVA) model that includes treatment (filgotinib 200 mg, filgotinib 100 mg, or placebo), stratification factors as fixed-effect factors, and baseline value as covariates will also be implemented. The estimated means of treatment effects and estimated differences in treatment effects between each filgotinib dose group and placebo will be presented with 90% CIs. Before the ANCOVA model is conducted, the following imputation will be performed:

- For change from baseline in segmental MaRIA score, if segmental MaRIA score is missing at Week 24, then corresponding segmental MaRIA score at baseline will be used to impute the missing value.
- For change from baseline in CDAI score, any missing CDAI component score will be imputed by LOCF method using the previous valid component score calculated at most recent analysis visit (eg, use the component score from Week 6 to impute missing component at Week 10, or use the component score from Week 18 to impute missing component at Week 24). If the component score from the most recent analysis visit is also missing, the missing value will be imputed with corresponding component score at baseline.

The observed mean change from baseline values for CDAI scores will be summarized and plotted over all analysis visits by treatment group.

In addition, subjects' small bowel disease status (remission, response, stable, and progression) based on MaRIA score will be summarized by treatment group for Week 24. A detailed definition of disease status in MaRIA score is provided in definition of terms.

CCI

CCI

A series of 12 horizontal black bars of varying lengths, decreasing from left to right. Each bar is preceded by a small black vertical tick mark.

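### SAP 6.2.2 compares 200 mg with the whole placebo group, which may include US males who could never be randomised to 200 mg; one supportive contrast limited to the 2:2:1 scheme would be a cheap, minor improvement.

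*SAP*

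**What the plan says.** Two allocation schemes operate. The general scheme is 2:2:1 to 200 mg, 100 mg and placebo. The exception covers US males without failure of two or more earlier biologics, with the qualifier that these are any TNF-alpha antagonist and vedolizumab. They "will be randomized in a 2:1 ratio to either filgotinib 100 mg or matching placebo" (Protocol synopsis, Study Design; the same rule is in Protocol 3.3), and SAP 1.2 repeats that they "will be randomized in a 2:1 ratio to receive either filgotinib 100 mg or matching placebo".

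The primary contrast in SAP 6.2.2, like Protocol 8.5.1, does not separate the schemes: "The difference in proportions between each filgotinib dose group and the placebo group will be presented along with the associated 90% CI". It is run on the Full Analysis Set, grouped as randomised (SAP 3.1.2, 3.2). SAP 3.4 adds: "There are no prespecified subject subgroupings for efficacy and safety analyses". SAP 6.3.2 reuses the method for binary secondary endpoints. Its ANCOVA for continuous endpoints has treatment, "stratification factors as fixed-effect factors, and baseline value as covariates will also be implemented".

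The three stratification factors are corticosteroid use, immunomodulator use and prior exposure to biologics. None is sex, country or failure of two biologics. SAP 3.3 mentions one scheme only: "Subjects will be randomly assigned to treatment groups via the interactive web response system (IWRS) in a 2:2:1 ratio using a stratified randomization schedule". SAP 5.2 tabulates dual failure separately for US males and other subjects, by treatment group. SAP 6.5 lists changed definitions and nothing on this point.

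**The concern.** A randomised comparison of 200 mg with placebo needs subjects who could have gone to either group. Restricted US males could go to placebo only, so any who are randomised to placebo have no randomised counterpart on 200 mg. They are defined by sex, country and treatment history, not by chance, so a different remission rate on placebo is possible. If it does differ, the 200 mg minus placebo difference is shifted and its 90% interval does not reflect the shift.

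The distortion would fall on one dose only. Protocol 1.4 says that two doses are studied in order to find the one with the most favourable risk/benefit profile, and the two differences will be shown side by side. The SAP 5.2 table would reveal an imbalance but not correct the estimate.

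**Working it through.** **The plan's own figure.** SAP 1.3 assumes 40% remission with n = 40. Clopper-Pearson at 90% for 16/40 gives 26.94% to 54.22%, which matches the stated 26.9% to 54.2%. That is a single-group precision figure and is not affected by this point.

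**Inputs from the documents.** Total 100; ratios 2:2:1 and 2:1; remission 40% on filgotinib and 20% on placebo (SAP 1.3), so an implied effect of 20 points.

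**Assumed inputs.** The documents give no number of restricted subjects, so I take m = 10, 20 or 30 of 100. They give no prognosis, so d (placebo remission in restricted minus eligible subjects) is taken as 10 or 20 points in either direction. SAP 6.2.2 names no interval method for the difference, so I use an unpooled Wald interval with z = 1.645.

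**Expected group sizes.** 200 mg = 0.4(100 - m). 100 mg = 0.4(100 - m) + 2m/3. Placebo = 0.2(100 - m) + m/3, where the first term is eligible for 200 mg and the second is restricted.

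| m | 200 mg | 100 mg | Placebo | Eligible / restricted placebo | Restricted share of placebo | Restricted share of 100 mg |
|---|---|---|---|---|---|---|
| 10 | 36 | 42.7 | 21.3 | 18 / 3.3 | 15.6% | 15.6% |
| 20 | 32 | 45.3 | 22.7 | 16 / 6.7 | 29.4% | 29.4% |
| 30 | 28 | 48 | 24 | 14 / 10 | 41.7% | 41.7% |

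The restricted share is equal in expectation in 100 mg and placebo, so that contrast stays balanced. In 200 mg it is zero.

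**Shift.** Size = restricted share of placebo x d. A positive d understates the 200 mg effect and a negative d overstates it.

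- 10-point gap: 0.156 x 10 = 1.6, 0.294 x 10 = 2.9, 0.417 x 10 = 4.2 points.
- 20-point gap: 3.1, 5.9 and 8.3 points.

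**Precision.** Half-width = 1.645 x sqrt(0.24/n200 + 0.16/n_pbo).

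- Planned contrast, whole placebo group: 19.6/19.8/20.3 points.
- Eligible-only contrast, placebo 18/16/14: 20.5/21.8/23.3 points.

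**Coverage of the planned nominal 90% interval** (normal approximation, Wald standard error from pooled placebo):

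- d = +10: 89.8/89.1/88.3%; d = -10: 89.8/89.0/88.0%.
- d = +20: 89.2/86.7/83.5%; d = -20: 89.1/85.9/81.5%.

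**Root mean squared error (RMSE).** Planned, squared: 0.24/n200 + [n_elig x 0.16 + n_restr x (0.2 + d)(0.8 - d)]/n_pbo² + (share x d)². Eligible-only, squared: 0.24/n200 + 0.16/n_elig.

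| | m = 10 | m = 20 | m = 30 |
|---|---|---|---|
| Eligible-only | 12.5 | 13.2 | 14.1 |
| Planned, d = +10 | 12.2 | 12.7 | 13.4 |
| Planned, d = -10 | 11.8 | 12.0 | 12.6 |
| Planned, d = -20 | 11.8 | 12.6 | 13.9 |

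The eligible-only contrast has the smaller error only when restricted placebo subjects remit at least 18.4/15.4/14.4 points more often than eligible ones.

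**The case against.** The case against giving this much weight is good, and most of it stands.

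- *The material case needs extreme inputs.* With eligible placebo remission at 20%, a gap of +20 puts restricted placebo remission at 40%, the rate that SAP 1.3 assumes on filgotinib; a gap of -20 puts it at 0%. Nothing in the documents supports gaps of that size. At 10 points the shift is 8% to 21% of the half-width.
- *The planned contrast is usually the closer estimate.* The RMSE figures agree, so the planned contrast should stay.
- *The problem may not arise.* About 80 centres in North America and Europe are planned, with no US share given. If no restricted subject enters, or prognosis is the same, there is no bias.
- *The study is descriptive.* No test depends on this difference. The estimate and its interval are, however, the main comparative outputs, so their validity still counts.
- *Partial handling and redaction.* SAP 5.2 will show the imbalance, and prior biologic exposure in the ANCOVA may absorb part of a prognostic difference for continuous endpoints. SAP 6.2.2 names no adjustment for the primary endpoint. Some text after SAP 6.3.2 is redacted, so a supportive analysis there cannot be excluded, though SAP 3.4 makes a hidden subgroup analysis unlikely.

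A reader might go further and infer that the 200 mg result will be biased, or that the eligible-only contrast should become primary. The documents support neither: the number and prognosis of restricted subjects are unknown, and the replacement would usually have the larger error.

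**Conclusion.** The gap in the text is certain and its consequence is conditional. The visible plan has no restriction or adjustment for 200 mg eligibility, and the 200 mg contrast can therefore include placebo subjects with no randomised counterpart. Bias arises only if restricted subjects enter and their prognosis differs. Its direction cannot be determined from the documents.

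Under the assumed 10% to 30% restricted share and a 10-point gap, the effect is small: at most 4.2 points against an implied effect of 20, with coverage no lower than 88.0%. It becomes material only when the restricted share is large and the gap is near 20 points. I rate this as a minor, worthwhile improvement and not as a defect that undermines the trial. The 100 mg versus placebo contrast and the exact interval in SAP 1.3 are not called into question.

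**What to change.** Before unblinding, add to SAP 6.2.2 one prespecified supportive contrast of 200 mg versus placebo for the primary endpoint, limited to subjects randomised under the 2:2:1 scheme. Report it beside the planned contrast, with placebo remission shown by 200 mg eligibility, and record the addition in SAP 6.5. Keep all subjects for 100 mg versus placebo. The planned contrast is unchanged, so Protocol 8.5.1 needs no amendment, and no change to dose or eligibility is proposed.

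The cost is a few lines of SAP text, one extra analysis and the wider interval shown above. The scheme used for each subject must be retrievable. SAP 4.1 states "The randomization schedule used for the study will be provided as an appendix to the CSR", but SAP 3.3 describes only the 2:2:1 schedule and no eligibility flag, so retrieval from the IWRS or the schedule should be confirmed first.

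I would not extend the change further. An eligibility term in the ANCOVA would rest on additivity, because no restricted subject is on 200 mg. Eligible-only contrasts for segment-level endpoints, which count remission or response only "among subjects with MaRIA score ≥ 7 in the same segment at Baseline" or on an equivalent condition, would leave very few placebo subjects: if 30% to 50% had a given segment active (an assumption), 0.3 x 14 = 4.2 to 0.5 x 18 = 9.0.
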